### 8.4.3 *Additional Analyses*

#### 8.4.3.1 *Objective Response Rate*

Objective response rate (ORR) is defined as the proportion of patients who had an objective response (unconfirmed). An objective response is defined as either complete response (CR) or partial response (PR), as determined by the investigator with use of RECIST v1.1. Patients not meeting these criteria, including patients without any post-baseline tumor assessments, will be considered non-responders. Confirmation is not required in this double-blind protocol, but for exploratory purposes ORR with confirmation by investigator will also be summarized. ORR must be sustained 28 days, when confirmation is reported.

The analysis population for ORR will be the ITT population. An estimate of BOR and ORR and its 95% CI will be calculated with the Clopper-Pearson method for each treatment arm. The difference in ORRs between the two treatment arms and 95% CI will be computed using the normal approximation to the binomial distribution and wald with continuity correction. The ORR will be also be compared between the two arms using stratified logistic regression. The sensitivity analysis will be computed using the stratified Cochran-Mantel-Haenszel test, stratified by the same factors used in the primary PFS and OS analyses (see Section 7.5.1).

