14.3.3 Additional Endpoints

Overall Response Rate (ORR)

ORR is defined as the percentage of patients with complete response (CR) or partial response (PR) according to the RECIST 1.1 criteria. Response confirmation is not required in this double-blind protocol. Patients with no on-study response assessments will be regarded as non-responders. The ORR will be compared between treatment arms by both the Fisher's exact test and a logistic regression analysis accounting for the randomization stratification factors.

Duration of Response (DOR)

For patients achieving a PR or a CR, the duration of response will be calculated as the time between the first documentation of a PR or a CR to the first documentation of PD or death, whichever occurs first. For patients achieving first a PR then a CR, the PR date will be the starting date for response duration calculation. For responders for whom a PD has not been documented yet, [Section 14.4.1](#) conventions regarding PD censoring will apply. Response duration will be descriptively presented by Kaplan Meier curve and median estimate for responders in each treatment arm.

Disease Control Rate (DCR)

DCR is defined as the summed percentage of patients with CR, PR and SD according to RECIST 1.1 criteria documented at least 8 weeks following treatment initiation.

Patient Reported Outcomes

Subjects will be assessed using the NCCN-Functional Assessment of Cancer Therapy (FACT) Kidney Symptom Index (FKSI-19) questionnaire and the EuroQoL 5D utility score (EQ-5D-5L). Details of the planned analyses for these outcomes will be provided in the SAP.

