14.5 Sample Size Estimation

A median PFS of 3.7 mo is estimated for the everolimus control group based on published data for 3rd line treatment of advanced ccRCC. The published data include non-randomized everolimus-specific PFS ([Heng 2015](#)), PFS across the 3rd line setting for all commonly used

agents (ibid.), and results from a Phase 3 randomized 3rd line study of dovitinib vs. sorafenib (GOLD study, [Motzer 2014](#)). In total across the IMDC database and the randomized GOLD study, these data represent 1490 unique patient outcomes specific to the 3rd line setting.

The proposed study of CBE vs. PboE will enroll patients with a 2:1 randomization between experimental and control arms with an accrual period of 8 mo and additional follow-up of 6 mo. If the control arm PFS is 3.7 mo and the true PFS hazard ratio of experimental patients to control patients is 0.60, the study will require approximately 42 experimental patients and 21 control patients in order to reject the null hypothesis of equal PFS between the two treatment arms with a power of 0.80. This estimation assumes a 1-sided type I error rate of 0.2, uniform accrual, exponential PFS distributions and the log-rank test for PFS comparison. The expected total PFS event count is 48 under the above assumptions.

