## **6.2 Determination of Sample Size**

A median PFS of 3.7 months is estimated for the everolimus control group based on published data for 3rd line treatment of advanced ccRCC (7). The proposed study of CBE vs. PboE will enroll approximately 63 patients with a 2:1 randomization between experimental and control arms with an accrual period of 8 months and additional follow-up of 6 months. If the control arm's median PFS is 3.7 months and the true PFS hazard ratio of experimental patients to control patients is 0.60, the study will require approximately 48 PFS events in order to reject the null hypothesis of equal PFS between the two treatment arms with a power of 0.80 and 1-sided type I error rate of 0.2 (exponential PFS distribution and log-rank test for PFS comparison).

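### The continuity-corrected Wald interval for the ORR difference is poorly calibrated for arms of about 42 and 21 with few responders, most visibly when control has none.

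*SAP*

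**What the plan says.** SAP 8.4.3.1 sets out the ORR analysis:

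- Population: "The analysis population for ORR will be the ITT population". Patients not meeting the response criteria, "including patients without any post-baseline tumor assessments, will be considered non-responders", so the denominators are the full arms.
- Within each arm, the estimate and its 95% CI "will be calculated with the Clopper-Pearson method for each treatment arm".
- Between arms, CBE minus PboE is reported with a two-sided 95% interval, obtained "using the normal approximation to the binomial distribution and wald with continuity correction".
- It also plans a stratified logistic regression, and a stratified Cochran-Mantel-Haenszel test as sensitivity analysis.

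No rule covers sparse or zero cells. Protocol 14.3.3 differs on the test: "The ORR will be compared between treatment arms by both the Fisher's exact test and a logistic regression analysis". SAP 8.4.3.1 does not carry Fisher's test forward.

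Protocol 14.5 plans "approximately 42 experimental patients and 21 control patients". Neither document states an ORR assumption, ORR power or alpha for ORR.

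**The concern.** The Wald variance is built from the observed proportions. A control arm of about 21 patients on everolimus may well have no responders. Its variance term is then zero, and only the fixed continuity correction represents uncertainty about the control rate. The same table would show a Clopper-Pearson upper limit of 16.1% for that arm, so the two error bars would sit oddly together.

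At stake is whether the reported interval for the ORR difference means what it says. It could look very precise when neither arm responds, or exclude zero where standard score-type intervals and the protocol's exact test do not. The stratified logistic regression would not help: with no control responders, its maximum-likelihood treatment estimate is infinite.

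**Working it through.** **Inputs.** n₁ = 42 (CBE) and n₂ = 21 (PboE), from Protocol 14.5; method from SAP 8.4.3.1. The plan gives no ORR figure to reproduce. The only combination response rate is 1/12 = 8.3% (Protocol 9.6). All control rates below are assumptions.

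**Formula.** The SAP does not write it out, so I use the usual form:

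d ± {1.96 × √[p₁(1−p₁)/n₁ + p₂(1−p₂)/n₂] + ½(1/n₁ + 1/n₂)}

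The correction is ½(1/42 + 1/21) = 0.0357.

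**Zero control responders.** With p₂ = 0 the second variance term vanishes.

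- 0/42: the half-width is the correction alone, so the interval is ±3.6 points.
- 6/42: p₁ = 0.1429, SE = √(0.1429 × 0.8571/42) = 0.0540, half-width = 1.96 × 0.0540 + 0.0357 = 0.1415. The interval is 0.0013 to 0.2844.

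| CBE (control 0/21) | Wald, corrected | Miettinen-Nurminen | Newcombe | Fisher, two-sided p |
|---|---|---|---|---|
| 0/42 | −3.6% to 3.6% | −15.7% to 8.5% | −15.5% to 8.4% | – |
| 6/42 | 0.1% to 28.4% | −2.2% to 28.0% | −2.9% to 27.8% | 0.166 |
| 7/42 | 1.8% to 31.5% | 0.1% to 30.7% | −0.9% to 30.6% | 0.085 |
| 8/42 | 3.6% to 34.5% | 2.4% to 33.4% | 1.1% to 33.3% | 0.044 |

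With 0 to 5 CBE responders the Wald interval includes zero. From 8 upward all methods agree. The first count to exclude zero is also 6 for arms of 40:20 and 46:23.

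**How likely these outcomes are.** If the control ORR is 2%, P(0/21) = 0.98²¹ = 65%; if 5%, 0.95²¹ = 34%. With control at 2% and CBE at 8.3–20%, the chance of exactly 6 or 7 against 0 is about 7–21%.

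**Exact coverage**, summing binomial probabilities over all 43 × 22 = 946 outcomes, for true rates of 0.5–30% with CBE at or above control:

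| | Mean | Minimum |
|---|---|---|
| Wald, corrected | 97.7% | 87.0% (4.5%/0.5%) |
| Miettinen-Nurminen | 96.1% | 94.6% |

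Coverage at 5%/1% is 90.6%. These dips come almost entirely from the 0/42 vs 0/21 outcome, because a true difference of 4.0 points lies outside ±3.6. At 4.5%/0.5% its probability is 0.955⁴² × 0.995²¹ = 0.1446 × 0.9001 = 0.130, leaving 87.0%. At 5%/1% it is 0.95⁴² × 0.99²¹ = 0.1160 × 0.8097 = 0.094, leaving 90.6%.

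Elsewhere the interval over-covers: 98.6% against 95.9% for the score interval at 10%/5%, 98.2% against 96.2% at 20%/5%, and 97.6% against 95.4% at 25%/10%.

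**False exclusion of zero under equal true rates.** Corrected Wald: 0.7% at 5%, 2.9% at 10%, 3.1% at 15%. Miettinen-Nurminen: 4.0%, 4.1% and 4.6%.

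**The case against.** The best defence is that the planned interval is usually conservative and that the replacement is not better everywhere. Much of this stands.

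- A reader might infer inflated type I error. The calculations do not show it. Two-sided false exclusion stays below 5% (at most 3.7% over equal rates up to 49.5%), and Miettinen-Nurminen excludes zero more often.
- A reader might infer that zero is wrongly excluded whenever control has no responders. It is not. The disagreement is confined to 6 CBE responders against Miettinen-Nurminen, and to 6 or 7 against Newcombe and Fisher. At 6/42 the lower limit clears zero by only 0.13 points.
- A reader might infer that the Wald interval is simply too wide. Its expected width is smaller at low rates: 26.4 against 29.7 points for Miettinen-Nurminen at 8.3%/2%, and 28.0 against 30.2 at 5%/5%. It is wider only at higher rates: 36.7 against 35.0 at 20%/5%, and 42.7 against 38.9 at 25%/10%.
- The score interval also over-covers at some low rates. At 8.3%/2% both cover about 98.1%; at 10%/2% it is 98.9% against 98.6% for Wald.
- Agreement with Fisher does not favour Miettinen-Nurminen overall. It excludes zero with Fisher p above 0.05 in 26 of the 946 outcomes, against 10 for Wald. One of them is 7/42 vs 0/21.
- No decision rule uses this interval. The positive-result rule is the PFS log-rank test.

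What remains is calibration. The planned interval swings from 87% coverage to well above 95%, and it is least trustworthy when a cell is empty.

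**Conclusion.** The point holds as a minor matter of analysis choice. For arms of about 42 and 21, the planned interval averages 97.7% coverage but can drop to 87.0%, while a standard score interval stays at or above 94.6% over the same range. With no control responders it is far too narrow at 0/42. At 6/42 it excludes zero when the two standard alternatives and the protocol's exact test do not.

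The size rests on three assumptions: the usual form of the corrected interval, arms close to plan, and true rates of 0.5–30%, with coverage averaged equally over that range. The documents give no control ORR, so how likely an empty control cell is remains uncertain. ORR is an additional endpoint; the primary PFS analysis and its conclusion are untouched.

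**What to change.** In SAP 8.4.3.1, replace the phrase naming the corrected Wald interval with one named method: the Miettinen-Nurminen score interval or the Newcombe interval. Keep Clopper-Pearson within each arm. Make the change before the unblinding described in SAP 8.8, so that the choice cannot appear to follow the data. In the same edit, the SAP could say whether the Fisher test in Protocol 14.3.3 is still planned.

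The cost is one phrase and a standard software option; no new data and no design change. There is a small statistical price: the new interval is wider on average at the lowest rates and, under equal true rates, the score interval excludes zero slightly more often, closer to the nominal 5%.

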#### 8.4.3.2 *Duration of Response*

Duration of Response (DOR) is defined as the time from the first documented objective response (PR or CR) to documented PD as determined by the investigator with use of RECIST v1.1 or death from any cause, whichever occurs first. Data for patients who are alive and who have not experienced disease progression at the time of the analysis will be censored at the date of the last evaluable tumor assessment. If no tumor assessments were performed after the date of the first occurrence of the objective response (CR or PR), DOR will be censored at the date of the first occurrence of the objective response. Censoring rules for DOR will follow those in **Table 2**. The determination of DOR is based on a non-randomized subset of patients (responders only), and formal hypothesis testing will not be performed. The subset of responders are defined based on post randomization outcomes therefore the responder population is not balanced across the two treatment arms. DOR will be estimated using Kaplan Meier (KM) methodology. Comparisons between treatment arms will be made using the stratified and unstratified log-rank test for descriptive purposes only.

DOR will be reported for patients with confirmed ORR.

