10.6.7 Tumor Assessments

Radiographic response and disease progression will be determined using RECIST version 1.1 and should employ diagnostic quality CT with intravenous contrast or MRI scans (see [Attachment 5](#) for methods of assessment discussion of CT and MRI).

Radiographic tumor assessments will include Chest/ Abdomen/ Pelvis (CAP). Diagnostic quality CT (or MRI) of chest/abdomen/pelvis with intravenous contrast will be performed for all patients at screening, every 8 weeks (± 5 days) from C1D1 for the first 12 cycles, and every 12 weeks (± 7 days) beyond 12 cycles on study. For patients deemed intolerant of intravenous CT contrast, a non-contrast CT of the chest may be obtained along with a contrast enhanced MRI of the abdomen and pelvis.

To ensure image consistency, the same imaging modality and acquisition protocols used at screening should be used for subsequent tumor assessments.

For the purpose of patient management and treatment decisions, radiographic response and disease progression will be assessed by investigators using RECIST v1.1 ([Attachment 5](#)).

Investigators are encouraged, if any doubt or ambiguities exist about radiographic progression, to continue study therapy if the patient is tolerating treatment, and repeat radiographic studies at the next scheduled time, and delay determination of progression until the findings indicating radiographic progression are unequivocal.

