##### 6.1.1.3 Additional Efficacy Endpoints

The additional efficacy endpoints are:

- Overall response rate (ORR), defined as the percentage of patients with complete response (CR) or partial response (PR) according to the RECIST 1.1 criteria per investigator.
- Duration of response (DOR), defined as the time between the first documentation of a PR or a CR to the first documentation of progressive disease (PD) or death, whichever occurs first as determined by RECIST 1.1 criteria per investigator.
- Disease control rate (DCR), defined as the summed percentage of patients with best overall response (BOR) of CR, PR and stable disease (SD) according to RECIST 1.1 criteria per investigator documented at least 8 weeks following treatment initiation.
- Patient reported outcomes using the NCCN-Functional Assessment of Cancer Therapy (FACT) Kidney Symptom Index (FKSI-19) questionnaire and the EuroQoL 5D utility score (EQ-5D-5L).

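### The SAP reports duration of response for confirmed responders, while the main ORR, the protocol and the SAP's own DOR definition all count unconfirmed responses

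*SAP*

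**What the plan says.** **Protocol 14.3.3** sets the rule for ORR: "Response confirmation is not required in this double-blind protocol". For DOR it covers every patient with a PR or CR, starts the clock at the first such assessment, and continues: "Response duration will be descriptively presented by Kaplan Meier curve and median estimate for responders in each treatment arm".

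**SAP 6.1.1.3** defines DOR as "the time between the first documentation of a PR or a CR to the first documentation of progressive disease (PD) or death", again without a confirmation condition.

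**SAP 8.4.3.1** defines ORR as unconfirmed. Of the confirmed version it says "for exploratory purposes ORR with confirmation by investigator will also be summarized", and adds "ORR must be sustained 28 days, when confirmation is reported".

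**SAP 8.4.3.2** opens with the same DOR definition, from the first documented response. It has a censoring rule that begins "If no tumor assessments were performed after the date of the first occurrence of the objective response"; such patients are censored at the response date. It then closes with "DOR will be reported for patients with confirmed ORR" and gives no reason for the restriction.

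**Protocol Attachment 5** says that best overall response will be programmed from Table C, whose title limits it to trials in which CR and PR need confirmation. The SAP does not cite Table C and gives no BOR rule of its own, although 8.4.3.1 reports BOR alongside ORR.

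**The concern.** ORR and DOR are normally read as a pair: how many patients responded, and for how long. Here the main ORR would count unconfirmed responders, while DOR would describe only those whose response was later confirmed.

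Any DOR set is selected on a post-randomization outcome, and the SAP acknowledges this for responders. Confirmation adds a second selection. The clock starts at first response, but a patient enters only if the response lasted until a later assessment. Short responses are therefore removed from DOR while still counting in ORR. A reader who put the two together would probably credit the ORR responders with more durable responses than they had.

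**Working it through.** **Comparison of the texts**

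| Place | Which responders |
|---|---|
| Protocol 14.3.3, ORR | Confirmation not required |
| Protocol 14.3.3, DOR | All with PR or CR, from first documentation |
| SAP 6.1.1.3, DOR | From first PR or CR, no confirmation condition |
| SAP 8.4.3.1, main ORR | Unconfirmed |
| SAP 8.4.3.1, confirmed ORR | Exploratory, sustained 28 days |
| SAP 8.4.3.2, definition and no-later-scan rule | Makes sense only if unconfirmed responders are included |
| SAP 8.4.3.2, closing sentence | Confirmed responders |

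A confirmed responder must have an assessment after the first response, so the no-later-scan rule could never apply to the set named in the closing sentence. SAP 8.4.3.2 is therefore inconsistent with itself as well as with the protocol.

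**Size of the selection effect**

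The documents give no DOR figure to reproduce. Assumption: DOR is exponential with true median m months.

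Confirmation intervals c, using the SAP's 30.4375 days per month:
- 28 days (SAP 8.4.3.1): 28/30.4375 = 0.92 months. This would need an unscheduled scan.
- 8 weeks, the interval "from C1D1 for the first 12 cycles" (Protocol 10.6.7): 56/30.4375 = 1.84 months.
- 12 weeks, the interval after cycle 12: 84/30.4375 = 2.76 months.

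Share of responders dropped because they progress or die before c: 1 − 0.5^(c/m). The exponential has no memory, so the median among those who last to c is m + c, and the shift equals c.

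| c | Dropped, m = 3 | m = 6 | m = 9 | Shift in median |
|---|---|---|---|---|
| 28 days | 19% | 10% | 7% | +0.92 months |
| 8 weeks | 35% | 19% | 13% | +1.84 months |
| 12 weeks | 47% | 27% | 19% | +2.76 months |

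If both arms confirm at the same interval, the difference in medians is (m₁ + c) − (m₀ + c) = m₁ − m₀, which is unchanged.

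**Can the direction reverse?**

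The SAP does not say whether PR followed by SD counts as sustained. Suppose it does not. Let a share p of the responders still progression-free at c be PR-then-SD with residual median r·m, and the rest have residual median m. The all-responder median is c + t, where t solves

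0.5^(c/m) × [p·0.5^(t/(r·m)) + (1 − p)·0.5^(t/m)] = 0.5.

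The confirmed-only median stays at m + c.

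| m, p, r | c | All responders | Confirmed only | Net shift |
|---|---|---|---|---|
| 6, 0.2, 2 | 28 days | 6.65 | 6.92 | +0.27 |
| 6, 0.2, 2 | 8 weeks | 6.52 | 7.84 | +1.32 |
| 9, 0.3, 4 | 28 days | 12.14 | 9.92 | −2.22 |
| 9, 0.3, 4 | 8 weeks | 11.69 | 10.84 | −0.85 |

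With r = 1 the shift stays at c. The values of p and r are illustrative and have no source in the documents.

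**Number of responders**

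Protocol 9.6 reports 1 PR among 12 evaluable ccRCC patients on the combination; Protocol 14.5 plans 42 and 21 patients. If that rate is applied to both arms, for scale only, the expected responders are 42/12 = 3.5 (CBE) and 21/12 = 1.75 (PboE).

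**The case against.** The best counter-argument is that the closing sentence adds an output rather than replacing one. It does not say that DOR is limited to confirmed responders. The text before it specifies Kaplan-Meier estimates and log-rank comparisons for responders, and 8.4.3.1 defines response as unconfirmed. The no-later-scan rule fits that reading. This has some force, but where the SAP adds a confirmed analysis for ORR it says so explicitly; for DOR it does not, and the closing sentence is the only one that names a reporting set. At best the set is ambiguous, and the wording still needs correction.

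Several further points stand in part:
- The sizes are assumption-driven. The 28-day row needs an unscheduled scan. The 12-week row concerns first responses around or after cycle 12, about 11 months (336/30.4375 = 11.04). Under the planning assumptions about 13% of control patients (0.5^(11.04/3.7)) and 29% of CBE patients (that value to the power 0.60) would still be progression-free then. The 8-week row is the most relevant.
- The Phase 1 rate comes from combination-treated patients, so applying it to the placebo arm is crude.
- With so few responders, any median DOR will be too imprecise for a shift of 1 to 2 months to carry much weight. Equally, losing one patient changes the set materially.
- Table C is reproduced guideline text with a self-limiting title, and it is a separate, weaker point. Even so, the attachment says in terms that BOR will come from it. A PR-then-SD patient would then be a responder for ORR with a BOR of SD.

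**Conclusion.** The concern holds. The closing sentence of SAP 8.4.3.2 conflicts with the protocol, with the SAP's endpoint definition, with the main ORR and with the censoring rule in the same section. If it is followed, DOR describes a different set of patients from ORR, selected further on how long the response lasted.

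The reported DOR is likely, though not certain, to be longer than that of the responders counted in ORR. Early progression alone would add about 1.8 months to the median under 8-week confirmation and an exponential DOR. Dropping PR-then-SD patients as well could shrink or reverse this.

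The consequence is limited. DOR is an additional, descriptive endpoint without formal testing; ORR, PFS, OS and the one-sided 0.2 decision are unaffected. This should be corrected, but it does not threaten the trial's main conclusion.

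**What to change.** 1. In SAP 8.4.3.2, replace the closing sentence so that DOR is reported for the same unconfirmed responders as the main ORR, as Protocol 14.3.3 has it. The no-later-scan censoring rule then applies as written.
2. State in the SAP that BOR is derived without confirmation, and correct the Table C reference in Attachment 5. If a protocol amendment is not wanted for this alone, the SAP sentence settles the derivation.
3. Show confirmed ORR, BOR and DOR together as one labelled exploratory set, and state there whether PR followed by SD counts as sustained.

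The cost is SAP wording, one cross-reference and one extra programmed output. The confirmed results are kept. The one drawback for the sponsor is that the headline DOR may be shorter.
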